7.7.3 Vital signs

Descriptive statistics of absolute values (and change from baseline) for vital signs (including body weight) will be provided by initial treatment and planned time or visit of the first treatment course and over all treatment courses.

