#### 5.2.4. Vital signs

Vital signs (blood pressure (BP) and pulse rate after 2 minutes supine rest) will be recorded at the screening visit and at the following time points: pre-infusion and 20 ( $\pm 5$ ), 65 ( $\pm 10$ ), 120 ( $\pm 30$ ) and 240 ( $\pm 30$ ) minutes after start of infusion of BI 6727, at every visit of the observation phase and at EOT.

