#### 6.2.2.2. Treatment Phase in repeated treatment courses

##### Visit 1 – day 1

Visit 1 – day 1, day of BI 6727 administration

- patient eligibility (in- and exclusion criteria)
- update of medical history

- physical examination including body weight, height, vital signs (blood pressure, pulse rate). Data from last visit of preceding course may be used in case examinations were done within the past 4 weeks.
- ECOG performance score
- laboratory examination including safety lab parameters (haematology including differential, biochemistry, coagulation parameters). Data from last visit of preceding course may be used in case examinations were done within the past 4 weeks.
- urine dipstick. Data from last visit of preceding course may be used in case examinations were done within the past 4 weeks.
- pregnancy test in women of childbearing potential
- changes in concomitant therapies
- occurrence of adverse events (AEs) since last visit

immediately before administration of BI 6727:

- resting ECG (series of three consecutive ECGs in third treatment course using dedicated equipment) at -0:15 min
- vital signs (blood pressure, pulse rate)

following administration of BI 6727 (start of infusion: 0:00) (the infusion rate needs to be constant during the whole infusion, deviations need to be documented in the eCRF. Duration (start and stop time of infusion) and actual dose administered need to be documented):

- resting ECG (series of three consecutive ECGs using dedicated equipment directly after completion of BI 6727 infusion (1h 15 min)
- vital signs (blood pressure, pulse rate) at 20 ( $\pm$  5 minutes), 65 ( $\pm$  10 minutes), 120 (2 hours;  $\pm$  30 minutes) and 240 minutes (4 hours;  $\pm$  30 minutes) after start of infusion
- Pharmacokinetic blood sampling: obtain blood samples 1:00 h (immediately prior to end of infusion of BI 6727) after start of infusion of BI 6727 (refer section 10.3 for sample handling). Blood samples have to be taken in the opposite arm of the infusion arm. For patients having central venous access, BI 6727 may be administered using this device and PK samples obtained from either forearm. The date and time of blood sampling must be recorded in the eCRF.
- adverse events occurring during and after infusion
- changes in concomitant therapy

Visit 2 – day 2

- vital signs (blood pressure, pulse rate)

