6.7 BASELINE, TIME WINDOWS AND CALCULATED VISITS

Study days and visits will be labelled according to the flow chart on page 6-8 of the CTP.

Unless otherwise specified, baseline is defined as the time-point closest to but prior to first administration of trial medication in the first treatment phase, where the first administration of trial medication is defined in [Section 6.3](#) above.

However, in the case of laboratory data, if the time is missing but the date of lab assessment is equal to the first medication date, [REDACTED]

[REDACTED]. This will then become the baseline value.

ECG

Baseline ECG is available from two courses. To account for possible variations between the study days, two different baseline definitions will be used:

1. Individual baseline is defined as the mean of the triplicate at the time-point closest to but prior to the start of the infusion of each treatment course, i.e. each treatment course has its own baseline.
2. Combined baseline is defined as the mean of the (two) triplicates at the time-point closest to but prior to the start of the infusion of both treatment courses, i.e. a common baseline is used for both treatment courses.

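### In repeated courses the vital-sign change from baseline mixes drift since course 1 with any change around the infusion, and no within-course change is planned

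*SAP*

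**What the plan says.** SAP 7.7.3 gives the whole vital-signs analysis in one sentence: "Descriptive statistics of absolute values (and change from baseline) for vital signs (including body weight) will be provided by initial treatment and planned time". The sentence goes on to cover "planned time or visit of the first treatment course and over all treatment courses". It sets no baseline for vital signs.

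SAP 6.7 supplies the default that applies when nothing else is specified: "baseline is defined as the time-point closest to but prior to first administration of trial medication in the first treatment phase". For ECG only, the same section departs from this. Its reason is: "To account for possible variations between the study days, two different baseline definitions will be used". Under the first ECG definition, "each treatment course has its own baseline"; the second is a combined baseline common to both courses.

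Protocol 5.2.4 says that blood pressure and pulse "will be recorded at the screening visit and at the following time points: pre-infusion and 20", 65, 120 and 240 minutes after the start of infusion, plus the observation visits and end of treatment. Protocol 6.2.2.2 repeats this for later courses. One vital-signs reading is listed under "immediately before administration of BI 6727", and the timed ones follow as "vital signs (blood pressure, pulse rate) at 20", 65, 120 and 240 minutes.

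**The concern.** The timed schedule brackets each infusion, and every repeated course has its own reading just before the drug is given. The planned change for those courses does not use that reading as its reference. It goes back to before the first dose of course 1, so whatever has moved between courses (disease, weight loss, other treatment, ordinary day-to-day variation) enters the change at 20 to 240 minutes together with anything that happened around the infusion.

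A reader of the change table for later courses could then take drift for an acute change, or miss an acute change that drift offsets. The SAP recognises between-day variation as a reason for a course-specific ECG baseline, but makes no such provision for blood pressure and pulse. The cohort given 1-hour and 2-hour infusions in courses 1 and 2, in either order (SAP 3.2), shows the difficulty most clearly: its course 2 change would combine infusion duration with drift, while its course 1 change would not carry that drift.

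**Working it through.** The documents give no figure for vital signs, so there is nothing to reproduce. The check sets the baseline rule against the measurement schedule.

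**1. Which baseline applies.** SAP 7.7.3 specifies none, so the SAP 6.7 default holds. In course 1 the closest value before the first dose is the scheduled pre-infusion reading, so course 1 changes already run from pre- to post-infusion. In course 2 onward the reference stays at course 1.

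**2. How old it is.** Protocol 3.3.3 allows a further course from 22 ± 2 days after the previous start and removes the patient if the gap exceeds 6 weeks. For course 2 the reference is therefore 22 - 2 = 20 days old at the least and 6 × 7 = 42 days at the most. For course 3 it is 40 to 84 days.

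**3. What the change contains.** Let B be the course 1 baseline, P the pre-infusion value of a later course and Y a timed reading in that course. Then

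Y - B = (P - B) + (Y - P) = drift + within-course change.

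With assumed values and B = 130 mmHg:

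| Drift | Within-course change | P | Y | Planned change Y - B | Same-course change Y - P |
|---|---|---|---|---|---|
| -10 | 0 | 120 | 120 | -10 | 0 |
| +10 | 0 | 140 | 140 | +10 | 0 |
| -10 | +5 | 120 | 125 | -5 | +5 |
| +10 | +5 | 140 | 145 | +15 | +5 |

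Over a drift of -10 to +10 mmHg the planned change runs from -10 to +10 with no acute change, and from -5 to +15 with an acute change of +5. The same-course change stays at 0 and +5.

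**4. Can the within-course change be read off the planned tables?** If rows are kept by course and planned time, the pre-infusion row shows P - B, that is, the drift. Subtracting it from a later row of group *means* gives the mean of Y - P exactly when the same patients contribute to both rows. But the statistics that SAP 7 lists for continuous variables, as far as the text can be seen, are N, minimum, quartiles, median and maximum, with no mean. These do not subtract. An invented example with three patients:

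| Patient | P - B | Y - B | Y - P |
|---|---|---|---|
| 1 | -10 | 0 | +10 |
| 2 | 0 | +10 | +10 |
| 3 | +10 | -10 | -20 |

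Both rows have median 0, minimum -10 and maximum +10, so the table looks flat. The within-patient changes have median +10 and minimum -20. Tables of absolute values have the same limit. If courses are pooled, which the wording of SAP 7.7.3 permits, the pre-infusion row no longer belongs to the same course and the separation is lost.

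**5. Spread, as illustration only.** Assume independent variation between days (SD d) and between readings on one day (SD r). The SD of the change is √(2(d² + r²)) against course 1 and √(2r²) against the same course, a ratio of √(1 + (d/r)²).

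- d = 10, r = 6 mmHg: √(2 × 136) = 16.5 against √(2 × 36) = 8.5, ratio 1.94.
- d = r: ratio √2 = 1.41.
- d = r/2: ratio √1.25 = 1.12.

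The documents give neither SD. The direction does not depend on them; the size does.

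**The case against.** A reader might infer that the plan presents drift between courses as an effect of the infusion. The documents do not support that. SAP 7.7.3 calls the quantity a change from baseline and attributes it to nothing, and Protocol 5.2.4 states no purpose for the timed readings.

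The rest of the opposing case has weight. Absolute values are tabulated too, and in a layout by course and time a flat profile that includes the pre-infusion row would point to drift. The layout cannot be seen: part of SAP 7 is blacked out. Change from the first pre-dose value is a proper measure of cumulative change, notably for body weight. ECG itself keeps a combined baseline as its second definition, so the SAP does not treat the course-specific one as the only right choice. The ECG work also has its own reason: QT prolongation in an animal model and a cohort added to study QTc. Heart-rate change is an ECG endpoint (SAP 5.3.5), so acute rate change is partly covered in courses 1 and 2 of that cohort and in courses 1 and 3 of the other patients. All analyses are descriptive.

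These arguments limit the harm but do not supply what is missing. The ECG endpoints do not cover blood pressure or every repeated course. Separate rows of medians and extremes do not show how far individual patients moved from before to after the infusion.

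**Conclusion.** The point holds as a minor gap in a descriptive safety table. By the SAP's own default, vital-sign changes in repeated courses are measured from before the first dose of course 1. They therefore mix drift with within-course change, and no within-course change is planned although the readings for it are scheduled. Drift enters one-for-one. How far it misleads depends on its size, which the documents do not give, and on whether the tables are by course and time or pooled. The mmHg figures above are illustrations under assumed values.

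Course 1 results are unaffected, and so is the MTD, which rests on first-course DLT. The conclusion assumes that the vital-signs schedule in the protocol of 3 October 2005 still stands after the three amendments that the SAP mentions, and that no blacked-out text sets another baseline for vital signs.

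**What to change.** In SAP 7.7.3 (or 6.7) add: for blood pressure and pulse at 20, 65, 120 and 240 minutes, the change from the same course's pre-infusion value will also be summarised, by course. Keep the first-dose baseline for visit-level values, body weight and cumulative change.

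Add a mapping rule. Protocol 6.2.2.1 (Visit 8) lets the day 22 visit coincide with day 1 of the next course, with shared examinations documented only once, under day 22. In that case use the day 22 value as the pre-infusion value of the new course. A day 22 value from an earlier date should not be used in this way.

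The cost is one more descriptive table, a sentence of SAP wording and a small programming step. No new data are needed.

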7.7.4 ECG

7.7.4.1 ECG - Assessment for patients of the extension cohort for additional QT/QTc analysis

All analyses described in this section will be performed using the Treated Set.

7.7.4.1.1 Central tendency analysis

The endpoint, QTcF change from individual baseline at each point in time (cf. [Section 5.3.1](#), endpoint 1, cf. [section 6.7](#)), will be analysed using a linear mixed-effects model for repeated measures data.

This model will include the following effects 'sequence', 'course', 'treatment' (both infusion types i.e. 1 hour duration and 2 hours duration) and 'time' as fixed, categorical effects, 'patient within sequences' as a random, categorical effect, the interaction effect 'treatment*time' as well as the continuous, fixed covariate of baseline value. The blocking effect specified by the SUBJECT variable within the repeated SAS statement (effect 'time') is patient*course implying that the values of 'time' are correlated within each subject's course. This model will use all observed data available. The variance covariance structure for the main analysis will be 'Compound symmetry'. Should the estimated G matrix be not positive definite, 'patient within sequences' will be included as fixed effect.

The endpoint, QTcF change from combined baseline at each point in time (cf. Section 5.3.1, endpoint 1, cf. section 6.7), will be analysed using the same model as described above, except that 'patient within sequences' will be removed from the model.

[figure not shown]
The SAS® procedure MIXED will be used involving the restricted maximum likelihood (REML)-estimation and the Kenward and Roger approximation of denominator degrees of freedom. Details of the programming code are described in the Analysis Data Set (ADS) plan, section 3 (Program Modules).

For the pairwise comparisons of the different treatments at each time-point the differences between the expected means for the BI 6727 infusions at each sampling point will be estimated by the difference in the corresponding Least-Squares Means and two-sided 90 % confidence intervals based on the t-distribution will also be computed. The 1-hour infusion is considered as the reference while the 2-hour infusion is considered as the test treatment, i.e. the difference '2-hour infusion - 1-hour infusion' will be computed.

The analysis described above will also be performed for the endpoints QTcF/HR change from baseline at each point in time.

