3.2 STATISTICAL DESIGN / MODEL

This phase I trial was performed according to an uncontrolled, open label, accelerated dose titration design to determine the MTD of BI 6727 in patients with advanced solid tumours.

The design is that of a 3+3 fixed dose escalation design ([R01-0028](#)) using a toxicity guided approach.

Patients with advanced solid tumours were eligible for this trial. BI 6727 was given as a short infusion over 60 minutes on day 1 of each three week treatment course during the escalation phase. The additional patients treated at the phase II recommended dose of 300 mg to investigate QTc changes, were assigned to one of two infusion time schedules: BI 6727-1h-infusion in course 1 and BI 6727-2h-infusion in course 2 or BI 6727-2h-infusion in course 1 and BI 6727-1h-infusion in course 2. The infusion schedule in courses 3 and higher was always the one hour infusion time.

Patients were not randomized, instead they were selected by the investigators and assigned to the cohort being filled at the time the patient was ready to enter the trial. Thus, the analyses will focus on the exploratory description of the results of each cohort, rather than comparing cohorts.

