4. CHANGES IN THE PLANNED ANALYSIS OF THE STUDY

Some newly created endpoints regarding tumour response are created and explained within the TSAP.

Following Amendment 3, a more extensive analysis of electrocardiograms (ECG) is planned on the additional cohort of 14 patients. The main aim of this cohort was to investigate QTc changes in parallel with PK sampling during and after intravenous infusion of BI 6727 300 mg dose over 1 hour and over 2 hours. For this set of 12 patients a different analysis of ECG data is planned (see [Section 7.7.4.1](#)).

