6.3 PATIENT SETS ANALYSED

Only one analysis population (Treated Set) will be considered for efficacy and safety (except ECG).

The Treated Set consists of all patients who received at least one application of the BI drug BI 6727.

Trial medication is defined as BI 6727.

First administration of trial medication is defined as date of first administration of BI 6727.

ECG

Per protocol set (PPS):

This is a subset of the Treated Set, restricted to patients, who have an ECG assessment in both courses (e.g. patients, who were replaced will be excluded).

[REDACTED]

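### In the combined-baseline QTcF model, removing the patient term makes the 90% CIs for 2-hour minus 1-hour treat a patient's two courses as independent

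*SAP*

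**What the plan says.** SAP 3.2 describes a two-sequence, two-course crossover for the additional patients at 300 mg. They are "assigned to one of two infusion time schedules: BI 6727-1h-infusion in course 1 and BI 6727-2h-infusion in course 2", or the reverse order.

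SAP 6.7 defines two ECG baselines. The individual baseline is specific to each course. The combined baseline averages the pre-infusion triplicates of both courses, so that "a common baseline is used for both treatment courses".

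SAP 7.7.4.1.1 models QTcF change from individual baseline with:
- fixed effects of sequence, course, treatment, time, treatment by time, and baseline;
- a random effect of patient within sequence;
- compound symmetry in the repeated statement, whose block "is patient*course implying that the values of 'time' are correlated within each subject's course".

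It adds a fallback: "Should the estimated G matrix be not positive definite, 'patient within sequences' will be included as fixed effect".

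The combined-baseline endpoint "will be analysed using the same model as described above, except that 'patient within sequences' will be removed from the model". No other block or patient-level term is substituted and no reason is given. Two-sided 90% CIs for 2-hour minus 1-hour are then planned at each time point.

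On numbers, SAP 4 first gives the additional cohort as 14 patients and then states: "For this set of 12 patients a different analysis of ECG data is planned". SAP 6.3 defines a per-protocol set of patients with ECGs in both courses, but SAP 7.7.4.1 says: "All analyses described in this section will be performed using the Treated Set".

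**The concern.** In the individual-baseline model, the patient effect is the only term that links a patient's two courses, because the repeated block stops at the course. Once it is removed, the model treats the 24 patient-courses of 12 patients as 24 independent units. The fixed-effect fallback goes with it.

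Subtracting one shared baseline does cancel the patient's usual QTcF level, but it does not make the two changes independent. A patient who responds strongly in one course may do so in the other, and both changes share the same baseline error; these push the correlation up. A day-to-day shift around the averaged baseline enters the two courses with opposite signs; this pushes it down. The baseline covariate takes up only the part of the correlation that is tied to baseline level.

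What is at stake is the set of intervals for the infusion-duration difference under one of the two baseline definitions. They can be too wide or too narrow. They will also be read beside the individual-baseline intervals, and a difference in width could come from the model and not from the baseline definition. HR is to be analysed in the same way, although the SAP does not say with which baseline.

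**Working it through.** The plan states no SD, power or CI width for this comparison, so there is no figure of its own to reproduce.

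**Inputs from the SAP.** 12 or 14 patients (section 4); two courses per patient (3.2); four post-baseline ECG times per course (5.3.5.1); two-sided 90% CI, compound symmetry within patient by course (7.7.4.1.1).

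**Assumed, in ms.** S = SD of patient-specific drug response; D = SD of the day-to-day shift; e = measurement SD; SD of patient baseline level 15.

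**Step 1: correlation.** Write QTcF in course j as patient level + day shift + response + error, and subtract the mean of the two course baselines. The patient level cancels. Then

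- Var = S² + D²/2 + 1.5e²
- Cov between courses = S² − D²/2 + e²/2
- ρ = Cov/Var

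Example, S/D/e = 8/8/5: Var = 64 + 32 + 37.5 = 133.5; Cov = 64 − 32 + 12.5 = 44.5; ρ = 0.33.

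**Step 2: standard error.** With n complete pairs, the variance of 2-hour minus 1-hour at one time is 2·Var·(1 − ρ)/n. The model as written takes 2·Var/n. The ratio of written to correct SE is therefore 1/√(1 − ρ).

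**Step 3: coverage.** Simulation of the balanced crossover, 6000 trials per setting, fixed effects as in the SAP, Satterthwaite df in place of Kenward-Roger. The last column is 12 pairs plus 2 one-course patients (12000 trials).

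| S/D/e | ρ | 1/√(1−ρ) | Simulated SE ratio, n=12 | Coverage, n=12 | Coverage, n=14 | Coverage, 12 pairs + 2 |
|---|---|---|---|---|---|---|
| 12/5/5 | 0.74 | 1.97 | 1.89 | 99.5% | 99.6% | 99.2% |
| 8/8/5 | 0.33 | 1.22 | 1.23 | 95.4% | 95.1% | 94.6% |
| 5/8/5 | 0.06 | 1.03 | 1.03 | 90.7% | 90.8% | 90.6% |
| 0/5/5 | 0.00 | 1.00 | 1.00 | 89.9% | 90.2% | 89.8% |
| 3/8/5 | −0.13 | 0.94 | 0.94 | 88.0% | 87.6% | not run |
| 0/8/4 | −0.43 | 0.84 | 0.84 | 82.9% | 82.7% | 83.6% |
| 0/12/5 | −0.54 | 0.80 | 0.82 | 81.5% | 81.9% | 81.6% |

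Mean CI half-width with n = 12, as written against patient as a fixed effect: 9.3 v 4.9 ms at ρ = 0.74; 4.8 v 4.9 ms at ρ = 0; 7.3 v 9.2 ms at ρ = −0.54.

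**Step 4: do the remedies work?** Over the 14 runs with complete pairs, coverage is 89.0–90.5% with patient as a fixed effect and 89.1–90.5% with the within-patient difference. With two one-course patients added, the within-patient difference gives 89.5–90.2%.

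**Step 5: sensitivity to the variance model.** A second set of assumed SDs, with a patient-by-course component and a separate baseline error, shows the same pattern with 12 patients. Coverage as written is 97.7%, 95.3%, 92.8%, 86.8% and 81.9% at ρ = 0.56, 0.31, 0.21, −0.22 and −0.48. With the patient link restored it is 89.7–90.2%. A small REML check (30 data sets, some with convergence warnings) gave an SE ratio of about 1.5 at ρ = 0.56; the formula gives 1/√(1 − 0.556) = 1.50.

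**The case against.** The strongest reply is that harm cannot be shown from the documents. They contain no QTcF variances. For ρ between −0.13 and 0.33, coverage stays between 87.6% and 95.4%. Both settings in the table with coverage below 87% assume no patient-to-patient variation in drug response. That is fair, but undercoverage does not need S = 0: at 5/12/5 (ρ = −0.26) coverage is 85.7%, although at 8/12/5 (ρ = 0.03) it is 90.3%. Where response variation dominates, the interval is too wide, which loses precision without overstating certainty.

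Nothing formal depends on these intervals. Protocol 7.2 and SAP 3.3 call all analyses descriptive and exploratory, the primary endpoint is DLT, and the supplied text attaches no QTcF margin or decision rule to the CI. The individual-baseline model, listed first, keeps the patient term. All of this stands and limits the consequence. Even so, SAP 4 makes QTc change under the two infusion durations the main aim of this cohort, and a descriptive 90% interval should still cover at about 90%.

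The removal may also have been deliberate. A common baseline strips out the stable patient level, so a random patient variance may be estimated at zero. That is a plausible motive, but it does not make ρ zero, the SAP does not state it, and the fallback in the first model already deals with that problem.

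Finally, the SAS code is in a separate analysis data set plan, and a figure after the quoted sentence is not reproduced in the supplied text. The program as run may differ. The printed sentence is explicit, so in that case the SAP text would need correcting.

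**Conclusion.** The point holds. As printed, the combined-baseline model sets the covariance between a patient's two courses to zero in a within-patient comparison, and no other section restores it. The SE, degrees of freedom and 90% CIs for 2-hour minus 1-hour are misspecified unless ρ happens to be near zero.

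The size depends entirely on assumed SDs. The effect is negligible near ρ = 0 and material when ρ is clearly away from it in either direction; the documents cannot say which case applies. The reading of the text is firm, the size is not. With complete balanced data the estimate itself is unaffected, and the MTD conclusion is not touched. The change should be made because it is cheap and alters reported intervals on this cohort's main question.

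**What to change.** For the combined-baseline endpoint, replace the removal of the patient term by one of:

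1. **Patient as a fixed effect**, as in the SAP's fallback for the first model. Sequence and the combined-baseline covariate are then aliased with patient, but 2-hour minus 1-hour stays estimable.
2. **Within-patient difference** (2-hour minus 1-hour) at each time, with sequence as a factor.

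Both allow either sign of ρ. Restoring only a random patient effect is not enough, because it cannot represent a negative correlation.

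State how one-course patients are handled, since the section uses the Treated Set and section 6.3 foresees replacements: they contribute nothing to option 2 and little to option 1. If the removal was intended, give the reason in the SAP.

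The cost is one or two sentences of SAP text and a few lines of SAS, with no new data. If ρ is truly zero, the price with 12 pairs is a CI about 2% wider under option 1 or 7% wider under option 2.
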